### **5.1.1.5 Infections**

On the basis of its mechanism of action, resulting in profound B-cell depletion, obinutuzumab may be associated with an increased risk of infections. Obinutuzumab should not be administered to patients with active infection, and caution should be exercised when including patients with a history of recurrent or chronic infections.

Serious bacterial, fungal, and new or reactivated viral infections can occur during and following the completion of obinutuzumab therapy. Fatal infections have been reported.

Reactivation of hepatitis B in patients with chronic hepatitis (HBsAg positive) with evidence of prior hepatitis B exposure, or in patients who are carriers (HBsAg negative and HBcAb positive) has been reported with other anti-CD20 antibodies. The risk is increased particularly when anti-CD20 antibodies are administered with immunosuppressive therapies, such as steroids or chemotherapy. Particular attention should be given to patients who have previously received highly immunosuppressive treatment, such as high-dose chemotherapy and SCT. Patients positive for HBsAg and HBcAb are not eligible for this study.

John Cunningham (JC) viral infection resulting in PML has been reported in patients treated with obinutuzumab. The diagnosis of PML should be considered in any patients presenting with new-onset neurologic manifestations. The symptoms of PML are unspecific and can vary, depending on the affected region of the brain. Motor symptoms with corticospinal tract findings (e.g., muscular weakness, paralysis, and sensory disturbances), sensory abnormalities, cerebellar symptoms, and visual field defects are common. Some signs or symptoms regarded as “cortical” (e.g., aphasia or visual-spatial disorientation) may occur. Evaluation of PML includes, but is not limited to, consultation with a neurologist, brain MRI, and lumbar puncture (cerebrospinal fluid testing for JC viral DNA). Additional guidelines for medical management of PML in this study are provided in [Table 19](#).

### **5.1.1.6 Immunizations**

The safety of immunization with live virus vaccines following obinutuzumab therapy has not been studied. Thus, vaccination with live virus vaccines is not recommended during treatment and until B-cell recovery.

### **5.1.1.7 Worsening of Preexisting Cardiac Condition**

In patients with underlying cardiac disease and treated with obinutuzumab, adverse events such as angina pectoris, acute coronary syndrome, myocardial infarction, heart failure, and arrhythmias, including atrial fibrillation and tachyarrhythmia, have been observed. These events may occur as part of an IRR and can be fatal. Therefore, patients with a history of cardiac disease should be monitored closely. In addition, these patients should be hydrated with caution to prevent a potential fluid overload.

### **5.1.1.8 Gastrointestinal Perforation**

GI perforation has been reported in patients with NHL treated with obinutuzumab, including fatal events. Patients with GI involvement should be monitored for signs of GI perforation.

### **5.1.2 Risks Associated with Rituximab**

The following adverse events are considered to be important risks associated or potentially associated with rituximab: IRRs, infections (including severe infections), PML, hepatitis B reactivation, neutropenia (including prolonged neutropenia), TLS, impaired immunization response, severe skin reactions (Stevens-Johnson syndrome/toxic epidermal necrolysis), and GI perforation. Details for these risks are provided below; refer to the Rituximab Investigator's Brochure for full information.

#### **5.1.2.1 Infusion-Related Reactions**

Acute IRRs are very common in patients receiving rituximab (occurring in  $\geq 10\%$  of patients) based on clinical trial experience. However, serious IRRs are uncommonly reported (occurring in  $\geq 1$  of 1,000 and  $< 1$  of 100 patients) and are rarely fatal (occurring in  $\geq 1$  of 10,000 and  $< 1$  of 1,000 patients). Most IRRs occur with the first administration of rituximab. Most IRRs are mild to moderate in severity (Grade 1/2) and can be managed by slowing or stopping the rituximab infusion. IRRs can be severe and in rare cases can result in death. Rituximab-induced IRRs consist of a cluster of symptoms and signs occurring during or within 24 hours of a rituximab infusion, which may be related to cytokine release and/or other chemical mediators, and these acute IRRs overlap with "cytokine release syndrome." Anaphylactic and other hypersensitivity reactions have been reported following rituximab administration, and clinical manifestations of these reactions are similar to cytokine release syndrome. In contrast to cytokine release syndrome, true hypersensitivity reactions typically occur within minutes of starting the rituximab infusion.

#### **5.1.2.2 Infections (Including Serious Infections)**

Serious infections, including fatal bacterial, fungal, and new or reactivated viral infections, can occur during and up to 1 year following completion of rituximab-based therapy.

#### **5.1.2.3 Hepatitis B Reactivation**

Reactivation of hepatitis B ranges from asymptomatic reactivations (detected by changes in laboratory parameters only) to fulminant liver failure and death. Patients with chronic hepatitis B (HBsAg positive) viral infection are at risk for reactivation and will be excluded from the study. Patients with evidence of prior hepatitis B exposure or who are carriers (defined as HBsAg negative and anti-HBcAb positive) are at a lower risk for reactivation. Patients who demonstrate evidence of reactivation while receiving an appropriate anti-viral therapy will be discontinued from study treatment.

#### **5.1.2.4 Progressive Multifocal Leukoencephalopathy**

Rare cases of PML have also been reported in patients treated with rituximab alone or in combination with other immunosuppressive medications ([Goldberg et al. 2002](#); [Calabrese et al. 2007](#); [Carson and Bennett 2009](#)). In a review of 57 patients who developed PML after rituximab administration, all patients had received prior therapies with alkylating agents, corticosteroids, purine analogs, or drugs to prevent allogeneic stem cell or solid-organ graft rejection. The diagnosis of PML in any patient treated with rituximab is rare, but it should be suspected in any patient who develops new-onset neurologic manifestations. The majority of patients with hematologic malignancies diagnosed with PML received rituximab in combination with chemotherapy or as part of a hematopoietic SCT. Most cases of PML were diagnosed within 12 months of the patients' last infusion of rituximab.

#### **5.1.2.5 Neutropenia (Including Prolonged Neutropenia)**

Neutropenia is very common in patients receiving rituximab (occurring in  $\geq 10\%$  of patients) based on clinical trial experience. However, delayed onset neutropenia is very rare (occurring in  $< 1$  of 10,000 patients), and the incidence of prolonged neutropenia is unknown. Neutropenia may lead to serious or overwhelming infection, especially if profound (Grades 3–4), prolonged, associated with breaches in natural mucosal barriers (e.g., diarrhea and/or mucositis), and/or other immunological defects (e.g., lymphopenia, hypogammaglobulinemia, and acquired immunodeficiency syndrome). Despite an increase in incidence of neutropenia and Grade 3–4 neutropenia associated with rituximab, most studies have not reported a significant increase in serious neutropenic infections.

#### **5.1.2.6 Tumor Lysis Syndrome**

Patients treated with rituximab may be at risk for TLS. Severe tumor TLS is very rare in patients receiving rituximab (occurring in  $< 1$  of 10,000 patients), based on postmarketing experience. Signs and symptoms (e.g., hyperuricemia, hyperkalemia, hypocalcemia, hyperphosphatemia, acute renal failure, and elevated LDH) that are consistent with TLS have been reported to occur after the first rituximab IV infusion in patients with high numbers of circulating malignant lymphocytes. A high number of circulating malignant cells ( $\geq 25,000/\text{mm}^3$ ) or high tumor burden confers a greater risk of TLS. For patients with evidence of TLS, rituximab should be discontinued, and the patient should be treated as clinically indicated.

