#### **4.3.2.1 Obinutuzumab**

[figure not shown]
Obinutuzumab will be administered by IV infusion at an absolute (flat) dose of 1000 mg on Days 1, 8, and 15 of the first cycle and on Day 1 of each subsequent cycle during induction treatment, and on Day 1 of every other month (i.e., every 2 months) during maintenance treatment (eligible patients with FL only) or during consolidation treatment (eligible patients with DLBCL only).

Obinutuzumab should be administered as an IV infusion through a dedicated line in an environment in which full resuscitation facilities are immediately available and under the close supervision of an experienced physician. Obinutuzumab infusions will be administered to patients according to the instructions outlined in [Figure 11](#) and [Figure 12](#). For patients with bulky lymphadenopathy, the infusion may be given extremely slowly over a longer period of time, or the dose may be split and given over more than 1 day.

No dose modification for obinutuzumab is allowed. Guidelines for treatment delays or discontinuation are provided in Section [5.1.8](#).

Premedication with a corticosteroid, antihistamine, and analgesic or antipyretic medication, as outlined in Section [4.3.2.5](#), is required to reduce the incidence and severity of IRRs. For anaphylaxis precautions, see [Appendix 10](#).

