**Table 6 Administration of First and Subsequent Infusions of Rituximab**

First Infusion (Day 1 of Cycle 1)	Subsequent Infusions

• Begin infusion at an initial rate of 50 mg/hr.

• If no infusion-related or hypersensitivity reaction occurs, increase the infusion rate in 50-mg/hr increments every 30 minutes to a maximum of 400 mg/hr.

• If a reaction develops, stop or slow the infusion. Administer medications and supportive care in accordance with institutional guidelines. If the reaction has resolved, resume the infusion at a 50% reduction in rate (i.e., 50% of rate being used at the time when the reaction occurred).

	

• If the patient experienced an infusion-related or hypersensitivity reaction during the prior infusion, use full premedication, including 100 mg of prednisone/prednisolone or 80 mg of methylprednisolone or equivalent (until no further IRR occurs); begin infusion at an initial rate of 50 mg/hr; and follow instructions for first infusion.

• If the patient tolerated the prior infusion well (defined by an absence of Grade 2 reactions during a final infusion rate of <math>\geq 100</math> mg/hr), begin infusion at a rate of 100 mg/hr. If no reaction occurs, increase the infusion rate in 100-mg/hr increments every 30 minutes to a maximum of 400 mg/hr.

• If a reaction develops, stop or slow the infusion. Administer medications and supportive care in accordance with institutional guidelines. If the reaction has resolved, resume the infusion at a 50% reduction in rate (i.e., 50% of rate being used at the time when the reaction occurred).

IRR = infusion-related reaction.

No dose modification for rituximab is allowed. Guidelines for treatment delays or discontinuation are provided in Section 5.1.

Premedication with a corticosteroid, analgesic/antipyretic, and antihistamine, as outlined in Section 4.3.2.5, is required to reduce the incidence and severity of IRRs. For anaphylaxis precautions, see Appendix 10.

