#### **4.6.2 Study Treatment Discontinuation**

Study treatment should be permanently discontinued in patients who experience any of the following:

- A DLT during the DLT window in patients enrolled in the dose-escalation phase
- Anaphylaxis, acute respiratory distress, or Grade 4 IRR
  - If a Grade 3 IRR is recurrent during the second and subsequent cycles, study treatment may be discontinued at the discretion of the investigator, following an individual benefit–risk assessment.
- Any adverse event that leads to a delay of more than 21 days in the start of the next treatment cycle

- Any hematologic adverse event that meets criteria for permanent discontinuation according to the guidelines provided in Section 5.1.8
- Hy's Law cases
- Grade  $\geq 3$  non-hematologic adverse event that has a reasonable possibility of being related to study treatment and either is life threatening or does not resolve to Grade  $< 2$  within 21 days
- Disease progression
- Pregnancy

In case of toxicity solely attributable to one drug of the combination requiring discontinuation, the other study drugs may be continued for patients experiencing clinical benefit as determined by the investigator after discussion with the Medical Monitor.

The primary reason for study treatment discontinuation should be documented on the appropriate eCRF.

Patients who discontinue study treatment will not be replaced, except as outlined below:

- During the dose-escalation phase, patients who discontinue study treatment prior to completing the DLT assessment window for reasons other than a DLT will be replaced by an additional patient at that same dose level.
- Patients who discontinue before having received at least one dose of each component of the combination will be replaced.

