## **5. ASSESSMENT OF SAFETY**

### **5.1 SAFETY PLAN**

The safety plan for patients in this study is based on clinical experience with study treatment components in completed and ongoing studies. The anticipated important safety risks of IMPs in this study (i.e., obinutuzumab, rituximab, idasanutlin, and venetoclax) are outlined below. Please refer to the Obinutuzumab, Rituximab, Idasanutlin, and Venetoclax Investigator's Brochures for a complete summary of safety information.

Several measures will be taken to ensure the safety of patients participating in this trial. Eligibility criteria have been designed to exclude patients at higher risk of toxicities (see Section 4.1). In addition, patients will undergo adequate safety monitoring during the study, as described in this section and in Section 4.5. Guidelines for managing adverse events, including criteria for dosage modification and treatment delays or discontinuation, are provided in Section 5.1.8.

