#### **5.1.5.5 Tumor Lysis Syndrome**

There is the identified risk of TLS with obinutuzumab or venetoclax treatment since these agents can result in the rapid destruction of a large number of tumor cells. Idasanutlin has been linked to tumor lysis events in AML patients. Therefore, overlapping toxicity in regard to TLS cannot be excluded. Guidelines for management of patients who develop TLS are provided in Section 5.1.6. Risks of TLS with rituximab are very low (see Table 14).

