**Table 18 Guidelines for Management of Non-Hematologic Toxicities**

Event	Action to Be Taken
General guidance for treatment delays, discontinuation, and resumption	
 
• If study treatment is withheld for > 21 days because of a toxicity that is attributable to study treatment, permanently discontinue study treatment.
 
• Permanently discontinue study treatment for Grade 4 events.
 
• When a treatment cycle is delayed because of toxicity resulting from any component of the regimen, all study treatment should be held and resumed together to remain synchronized.
 
• Dosing may be resumed after resolution to Grade <math>\leq 1</math> or baseline status. Resumption of dosing without complete resolution of toxicity may be considered in special circumstances after having obtained Medical Monitor agreement.
 

IRRs and anaphylaxis	
 
• Guidelines for the management of IRRs are provided in Section 5.1.1.1. In case of Grade 4 IRRs or anaphylaxis, study treatment should be permanently discontinued.
 

Clinical and laboratory TLS	
Grade 4 events:
 
 
• Permanently discontinue study treatment in the case of Grade 4 events.
 
 
Grade <math>\leq 3</math> events:
 
 
• Withhold study treatment. a
 
• Correct electrolyte abnormalities, monitor renal function and fluid balance, and administer supportive care, including dialysis as indicated.
 
• If symptoms (laboratory and clinical) have resolved completely, resume obinutuzumab or rituximab at full dose and resume venetoclax and idasanutlin at current dose.
 

New-onset neurologic manifestations suggestive of PML	
 
• Withhold study treatment. a
 
• Consult with a neurologist if PML is suspected (refer to Section 5.1.1.5 for guidance on investigations).
 
• If PML is ruled out, resume obinutuzumab or rituximab at the full dose and resume idasanutlin and venetoclax at the current dose.
 
• If PML is confirmed, permanently discontinue study treatment.
 

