**Table 19 Guidelines for Management of Toxicities That Occur during Maintenance or Consolidation Treatment**

Event	Action to Be Taken
Hematologic toxicity: Grade 3 or 4	

• Withhold study treatment.

• Administer myeloid growth factors for neutropenia as allowed according to institutional guidelines.

• Administer RBCs or platelets as required.

• If improvement to Grade <math>\leq 2</math>, resume obinutuzumab or rituximab at full dose and resume venetoclax at next lower dose for subsequent cycles per guideline in Section 5.1.8. Patients who are not eligible for further venetoclax dose reductions should be permanently discontinued.

• If study treatment is withheld for <math>> 42</math> days, permanently discontinue study treatment.

• Withdraw venetoclax and idasanutlin in case of recurrent episodes of Grade <math>\geq 3</math> thrombocytopenia and/or neutropenia.

Non-hematologic toxicity: Grade $\geq 2$	

• Withhold study treatment.

• If improvement to Grade <math>\leq 1</math> or baseline, resume obinutuzumab or rituximab at full dose and resume venetoclax at the next lower dose for subsequent cycles per guideline in Section 5.1.8. Patients who are not eligible for further venetoclax and/or idasanutlin dose reductions should be permanently discontinued.

• If study treatment is withheld for <math>> 42</math> days, permanently discontinue study treatment.

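### Section 5.1.2.6 stops rituximab for any tumor lysis syndrome, while Table 18 restarts it once Grade 3 or lower events resolve; 5.1.2.6 should be conformed to Table 18

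*Protocol*

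**What the plan says.** Protocol Section 5.1.2.6, the TLS entry among the rituximab risks, ends: "For patients with evidence of TLS, rituximab should be discontinued, and the patient should be treated as clinically indicated". It states no grade, no condition for restarting and no cross-reference.

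Table 18 (Section 5.1.8.1, induction) has a row for clinical and laboratory TLS. Grade 4 events stop study treatment permanently. For Grade 3 or lower, treatment is withheld and the abnormalities are corrected; then "If symptoms (laboratory and clinical) have resolved completely, resume obinutuzumab or rituximab at full dose and resume venetoclax and idasanutlin at current dose".

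Table 19 covers consolidation. After a Grade 2 or higher non-hematologic event has improved to Grade 1 or lower or to baseline, sites "resume obinutuzumab or rituximab at full dose and resume venetoclax at the next lower dose for subsequent cycles per guideline in Section 5.1.8".

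On where the stopping rules are kept:

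- Section 5.1, opening text: "Guidelines for managing adverse events, including criteria for dosage modification and treatment delays or discontinuation, are provided in Section 5.1.8".
- Section 4.3.2.2, rituximab dosing: "No dose modification for rituximab is allowed. Guidelines for treatment delays or discontinuation are provided in Section 5.1".
- Section 4.3.2.1, obinutuzumab dosing: "No dose modification for obinutuzumab is allowed. Guidelines for treatment delays or discontinuation are provided in Section" 5.1.8.
- Section 5.1.5.5, overlapping TLS risk: "Guidelines for management of patients who develop TLS are provided in Section 5.1.6. Risks of TLS with rituximab are very low".
- Section 4.6.2 lists the events that require permanent discontinuation. TLS is not named. The nearest item is a Grade 3 or higher "non-hematologic adverse event that has a reasonable possibility of being related to study treatment and either is life threatening or does not resolve to Grade" below 2 within 21 days.

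**The concern.** A site reading only the rituximab risk section would stop the antibody on any evidence of TLS and find nothing about restarting. A site reading Table 18 would give it again at full dose once Grade 3 or lower TLS had cleared. The same resolved event could therefore be handled in two ways. The trigger in 5.1.2.6 is evidence of TLS, whatever drug caused it, so TLS driven by venetoclax also sets it off.

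What is at stake is patient management. A patient with TLS in Cycle 1 could lose up to five later rituximab infusions (Cycles 2 to 6), plus consolidation rituximab if in CR or partial response at end of induction. If the sponsor does not want re-challenge, the opposite error is a full-dose restart that nobody intended.

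**Working it through.** **1. Where the texts agree and differ.** Both stop rituximab while TLS is present. Neither restarts it after Grade 4. They part only on Grade 3 or lower TLS that has resolved completely and meets no other permanent-stop rule: 5.1.2.6 is silent on restarting, and Table 18 restarts at full dose.

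**2. Which rule governs.** Four features favor Table 18.

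- The opening of Section 5.1 assigns discontinuation criteria to Section 5.1.8. The broader pointer in Section 4.3.2.2 leads to that same opening text.
- The action rules normally say *permanently* when a stop is final (Sections 3.1.2, 4.6.2 and 5.1.8; Tables 16, 18 and 19). Section 5.1.2.6 does not.
- The Section 4.6.2 list does not name TLS.
- Table 18 carries a rituximab-specific permanent stop for Stevens-Johnson syndrome and toxic epidermal necrolysis, and none for TLS.

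**3. Why the sentence still needs changing.** No sentence says that Table 18 overrides 5.1.2.6. Section 5.1.2 is also not pure background. Its hepatitis B entry (5.1.2.3) contains a stop rule that has no row in Table 18 and is not named in 4.6.2. Plain *discontinue* is not reliably temporary either: Section 5.4.3.1 uses it for pregnancy, which 4.6.2 lists as a permanent stop. Section 5.1.6, to which 5.1.5.5 sends the reader for TLS, does not mention rituximab, and neither does Appendix 12.

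**4. Who is affected.** Only DLBCL patients on rituximab, in the bridging and expansion cohorts. In bridging cohorts, Grade 3 clinical TLS in Cycles 1 and 2 that is judged clearly unrelated to the lymphoma is a DLT (Section 3.1.2.1) and ends study treatment anyway (Sections 3.1.2 and 4.6.2).

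**5. Size.** Inputs:

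- n = 40 DLBCL expansion patients (Section 6.1.2).
- r = TLS rate. Table 14 shows 2% for venetoclax monotherapy and <1% for rituximab monotherapy. I use 2%, with 3% as an upper bound from adding the two.
- f = share of TLS in the disputed group. The documents do not give it; I assume 25% to 100%.

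Expected number = 40 × r × f. Chance of at least one = 1 − (1 − r × f)^40, taking patients as independent.

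| r | f | Expected | P(at least one) |
|---|---|---|---|
| 2% | 25% | 40 × 0.02 × 0.25 = 0.2 | 1 − 0.995^40 = 18% |
| 2% | 50% | 40 × 0.02 × 0.50 = 0.4 | 1 − 0.99^40 = 33% |
| 2% | 100% | 40 × 0.02 × 1 = 0.8 | 1 − 0.98^40 = 55% |
| 3% | 25% | 40 × 0.03 × 0.25 = 0.3 | 1 − 0.9925^40 = 26% |
| 3% | 100% | 40 × 0.03 × 1 = 1.2 | 1 − 0.97^40 = 70% |

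**6. Effect on the CR proportion.** Even if every affected patient's response flipped, the expected shift at r = 2% is at most (40 × r × f)/40 = r × f, or 0.5 to 2.0 percentage points. Table 21 gives a 90% CI of 0.40 to 0.68 at an observed 55%, a width of 28 points.

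**The case against.** The strongest reply is that there is no real conflict. Section 5.1.2 describes risks, and the missing pointer is the style of its subsections. The Stevens-Johnson entry in that section has no action rule at all; its stop is in Table 18. Section 5.1.2.6 pairs stopping rituximab with treating the patient, which reads as acute management. Table 18 also stops the drug and then supplies the restart rule on which 5.1.2.6 is silent.

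Divergence between sites is limited too. TLS of any grade is an adverse event of special interest, reportable within 24 hours (Section 5.2.3). Section 4.6.2 allows the other drugs to continue when a toxicity solely attributable to one drug requires its discontinuation, if the patient is benefiting and after discussion with the Medical Monitor. Dropping rituximab alone is therefore not automatically a breach of the Table 18 rule that a delayed cycle's drugs are held and resumed together.

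Most of this stands, and it settles which rule governs. It does not make the sentence correct: on its face 5.1.2.6 applies at every grade with no way back, and the hepatitis B entry shows that this section does hold working stop rules.

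Two stronger readings are tempting. A reader might infer that 5.1.2.6 imposes a permanent stop at all grades. The documents do not support that: the word *permanently* is absent, 4.6.2 does not list TLS, and Table 18 names rituximab among the drugs to restart. A reader might also infer that the protocol leaves the governing rule open. It does not, because the opening of Section 5.1 sends discontinuation criteria to 5.1.8.

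**Conclusion.** The sentence in 5.1.2.6 is wrong as written and should be conformed to Section 5.1.8. Severity is low. It is a patient-management inconsistency limited to rituximab-treated DLBCL patients, expected to touch 0.2 to 0.8 of 40 expansion patients, or 0.3 to 1.2 at the 3% upper bound.

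These figures assume that a monotherapy TLS rate carries over to the triplet and that 25% to 100% of TLS falls in the disputed group. The documents establish neither. Table 14 shows 2% for TLS overall and 2% for Grade 3 or higher, so lower-grade TLS is not visible at that rounding.

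A reader might infer that uneven antibody exposure threatens the primary endpoint. The numbers do not support that: an expected shift of at most 0.5 to 2.0 points at the 2% rate is negligible beside a 28-point interval.

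**What to change.** Replace the last sentence of Section 5.1.2.6 with:

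> For patients with evidence of TLS, withhold rituximab, treat as clinically indicated, and follow Section 5.1.8 (Table 18 TLS row during induction; Table 19 during consolidation) for resumption or permanent discontinuation, unless the event is a DLT or meets a permanent-discontinuation criterion in Section 4.6.2.

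Both tables have to be named because Table 18 covers induction only. Narrowing the pointer in Section 4.3.2.2 from 5.1 to 5.1.8, to match the obinutuzumab text, is an optional clerical tidy-up. If the sponsor does not want re-challenge after TLS, that is a separate clinical decision, and the stop belongs in Tables 18 and 19.

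The cost is one sentence in the next protocol amendment, with no change to design, sample size or analysis.
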